1.2.2. Ovarian Cancer and Standard Treatment

Ovarian Cancer (OC) is a lethal disease with a 5 years survival rate of 20-30% for advanced OC. It is the second leading cause of cancer related deaths in women. A large proportion of patients with OC are diagnosed at an advanced tumor stage.

The outcome after chemotherapy for advanced OC becomes poorer and poorer each time a new treatment is introduced following progression on the previous treatment. Approximately 14,000 OC patients die each year due to disease progression.

Treatment of OC and breast cancer (BC) progressed when the genes BRCA1 and BRCA2 were cloned in the early 1990s and allowing identification of high risk individuals. These genes encode proteins that are involved in DNA homologous recombination (HR) (14). Epidemiological studies have shown an association between germline BRCA1/2 (gBRCA1/2) mutations and the development of OC, (BC), and to a lesser extent pancreatic and endometrial cancers. Mutation frequencies are estimated to be approximately 15-20% for those diagnosed with OC and 5% for those diagnosed with BC (15). In a recent publication it was shown that for BRCA1 and 2 carriers, cumulative risk for BC by age 80 was 72% and 69%, respectively. For OC, cumulative risk was 44% and 17%, respectively.

The peak incidence of BC occurred in the 41-50-year age group (28.3 per 1000 person-years) for BRCA1 and in the 51-60-year group (30.6 per 1000) for BRCA2 mutation carriers. The incidence of OC was 3.6 times higher for BRCA1 than BRCA2 carriers, with the peak incidence of cancer occurring regardless of mutation type among women in the 61-70-year age group (29.4 per 1,000 in BRCA1 carriers). For BRCA1 and 2 carriers, BC risk increased with the number of first- and second- degree relatives with breast cancer. In contrast, OC risk did not vary with respect to family history of this disease (16). Patients harboring germline BRCA1/2 mutations carry a defective copy of the gene in every cell, which increases the likelihood of cancer developing if the remaining copy becomes defective through somatic mutation or epigenetic inactivation (17). DNA repair pathways involving BRCA1/2 engage in single or double stranded DNA breaks, which can occur from damage inflicted by ultra violet light, the generation of reactive oxygen species, ambient or therapeutic irradiation, day- to-day replication errors or chemical exposure (18). Cells lacking a functional BRCA1/2 are also deficient in HR and show a high-degree of chromosomal instability as well as increased sensitivity to ionizing radiation and chemotherapeutic agents that lead to double-stranded breaks (19-21).

1.2.3. PARP inhibitors PARP inhibitors in Ovarian Cancer

Poly(ADP-ribose) polymerases (PARPs) are a family of DNA-dependent nuclear enzymes catalyzing the transfer of ADP-ribose moieties from cellular nicotinamide-adenine-dinucleotide (NAD⁺) to a variety of target proteins. There are 17 PARP family member proteins identified through sequence homology of the catalytic domain. PARP1, 2 and 3 have all been implicated in

DNA repair, with PARP1 being the most abundant (22). PARP inhibitors are designed to compete with NAD⁺ for the substrate binding to PARP and inhibit PARP activity (23). Cells containing dysfunctional BRCA1 or BRCA2 have been shown to become profoundly sensitized to the inhibition of PARP enzymatic activity, resulting in chromosomal instability, cell cycle arrest and subsequent apoptosis (24). PARP inhibition is thought to induce synthetic lethality, which describes a process where at least two genetic lesions that individually are not lethal become lethal when combined in the same cell (25). For example, cells that are deficient in HR, which is not lethal in itself, are hypersensitive to a reduction in PARP activity by PARP inhibitors (14,15-21). However, disruption to other proteins involved in HR DNA repair other than in BRCA may have the same effect on PARP inhibitor sensitivity (26). A further important mechanism of action for PARPi is the trapping of the PARP1 and PARP2 enzymes at damaged DNA causing cytotoxicity (27). Recent studies have revealed a more complex web of fundamental cellular processes that PARP1 is involved other than in DNA repair such as chromatin remodeling and transcription or regulation of the cell cycle (28).

There are currently three PARP inhibitors approved, for either monotherapy or maintenance therapy in patients with advanced OC. Two are approved in patients with BRCA 1 and 2 mutations with advanced OC having undergone therapy with >3 chemotherapies (Olaparib) or >2 chemotherapies (Rucaparib). All three PARPi are approved as maintenance therapy in patients with advanced OC who are in complete or partial response to platinum based chemotherapy.

The effectiveness of PARP inhibitors as monotherapy or as maintenance therapy has substantially improved the progression free survival and overall survival in OC patients. PARP inhibitors as single agents or as potential enhancers of cytotoxic agents that provoke DNA damage, such as alkylating agents and chemotherapy (18) have been investigated in a number of studies.

1.3. NAME AND DESCRIPTION OF THE INVESTIGATIONAL PRODUCT

[REDACTED]

1.4. SUMMARY OF PRIOR PRE-CLINICAL AND CLINICAL STUDIES

[REDACTED]

The image consists of a single, uniform black rectangle that fills the entire frame. There are no discernible features, text, or patterns other than the solid black color.

[REDACTED]

[REDACTED]

[REDACTED]

[REDACTED]

[REDACTED]

[REDACTED]

[REDACTED]

[REDACTED]

[REDACTED]

[REDACTED]

[REDACTED]

[REDACTED]

[REDACTED]

[REDACTED]

[REDACTED]

[REDACTED]

[REDACTED]

[REDACTED]

[REDACTED]

[REDACTED]

[REDACTED]

[REDACTED]

[REDACTED]

[REDACTED]

[REDACTED]

[REDACTED]

[REDACTED]

[REDACTED]

[REDACTED]

[REDACTED]

[REDACTED]

[REDACTED]

[REDACTED]

[REDACTED]

[REDACTED]

[REDACTED]

[REDACTED]

[REDACTED]

[REDACTED]

[REDACTED]

[REDACTED]

[REDACTED]

[REDACTED]

[REDACTED]

[REDACTED]

[REDACTED]

[REDACTED]

[REDACTED]

[REDACTED]

[REDACTED]

[REDACTED]

[REDACTED]

[REDACTED]

[REDACTED]

[REDACTED]

[REDACTED]

[REDACTED]

[REDACTED]

[REDACTED]

[REDACTED]

[REDACTED]

[REDACTED]

[REDACTED]

[REDACTED]

[REDACTED]

[REDACTED]

[REDACTED]

[REDACTED]

[REDACTED]

[REDACTED]

[REDACTED]

[REDACTED]

[REDACTED]

[REDACTED]

[REDACTED]

- [REDACTED]
- [REDACTED]
- [REDACTED]

[REDACTED]

- [REDACTED]
 - [REDACTED]
 - [REDACTED]
 - [REDACTED]
 - [REDACTED]
- [REDACTED]
- [REDACTED]

- [REDACTED]
 - [REDACTED]

- [REDACTED]
 - [REDACTED]
 - [REDACTED]

- [REDACTED]
 - [REDACTED]
 - [REDACTED]
 - [REDACTED]
 - [REDACTED]
 - [REDACTED]
 - [REDACTED]
 - [REDACTED]
 - [REDACTED]

- [REDACTED]
 - [REDACTED]

- [REDACTED]
 - [REDACTED]

[REDACTED] [REDACTED]

[REDACTED]

[REDACTED]

[REDACTED]

[REDACTED]

[REDACTED]

[REDACTED]

[REDACTED]

[REDACTED]

[REDACTED]

[REDACTED]

[REDACTED]

[REDACTED]

[REDACTED]

[REDACTED]

[REDACTED]

- [REDACTED]
- [REDACTED]
- [REDACTED]
- [REDACTED]
- [REDACTED]
- [REDACTED]
- [REDACTED]
- [REDACTED]

[REDACTED]

[figure not shown]
[REDACTED]

[REDACTED]

[REDACTED]

[REDACTED]

[REDACTED]

1.5. RISKS / BENEFITS ASSESSMENT

The inclusion and exclusion criteria, screening, and safety monitoring practices employed by this protocol, and physical examination are adequate to protect the subject's safety and detect all TEAEs.

1.5.1. Pregnancy

Any pregnancy that occurs while taking study drug should be recorded using a Pregnancy Report Form and reported immediately to Sponsor within 24 hours of learning of the pregnancy. See [Section 9.5](#) for more information on reporting of pregnancy.

1.5.2. Unknown Risks

Research inherently carries the possibility of risks that are unknown or that cannot be foreseen based on current information.

1.5.3. 2X-121

In the phase 1 study, fatigue was the dose limiting toxicity. Apart from fatigue in the phase 1 study as well as in the two ongoing phase 2 studies, the most frequent treatment-emergent adverse events are gastrointestinal related (nausea, diarrhea, loss of appetite and vomiting). Phototoxicity and allergic reactions with maculo-papular rash and periorbital edema are seen.

Refer to the Investigator's Brochure for a complete list of risks associated with 2X-121.

1.5.4. Dovitinib

Across the various dovitinib studies, the most commonly reported non-laboratory AEs for both continuous dosing and 5 days on/2 days off dosing, were nausea, fatigue, diarrhea, vomiting and decreased appetite. Commonly reported AEs were reversible and manageable; most were mild or moderate in severity (CTCAE grade 1 or 2).

Refer to the Investigator's Brochure for a complete list of risks associated with dovitinib.

1.5.5. Benefits

Subjects participating in this study will contribute to the development of a drugs which has the potential to become a treatment option for them and others in the future.

[REDACTED]

[REDACTED]

[REDACTED]

[REDACTED]

[REDACTED]

[REDACTED]

- [REDACTED]
[REDACTED]
- [REDACTED]
[REDACTED]
- [REDACTED]
[REDACTED] [REDACTED]
[REDACTED]
[REDACTED] [REDACTED]
[REDACTED]

1.6.2. Rationale for Dose Selection

[REDACTED] [REDACTED]

[REDACTED]
[REDACTED]
[REDACTED]
[REDACTED]
[REDACTED]

[REDACTED]
[REDACTED]

[REDACTED]
[REDACTED]
[REDACTED]
[REDACTED]
[REDACTED]
[REDACTED]
[REDACTED]

[REDACTED]
[REDACTED]
[REDACTED]
[REDACTED]
[REDACTED]
[REDACTED]
[REDACTED]

[REDACTED]
[REDACTED]
[REDACTED]
[REDACTED]
[REDACTED]
[REDACTED]

[REDACTED]
[REDACTED]
[REDACTED]
[REDACTED]
[REDACTED]

[REDACTED]
[REDACTED]
[REDACTED]
[REDACTED]

[REDACTED]

[REDACTED]

[REDACTED]

[REDACTED]

[REDACTED]

[REDACTED]

2. STUDY OBJECTIVES AND OUTCOME MEASURES

2.1. STUDY OBJECTIVES

2.1.1. Primary Objective

The primary objective of this study is:

Part 1

- To determine the maximum tolerated dose (MTD) of 2X-121 monotherapy given twice daily (BID) in patients with advanced solid tumors.

Part 2

- To determine the MTD of dovitinib given in combination with 2X-121 (MTD) in patients with advanced solid tumors.

2.1.2. Secondary Objective

The secondary objectives of this study are:

- To evaluate the anti-tumor activity of 2X-121 monotherapy (Part 1) and in combination with dovitinib (Part 2) in patients with advanced solid tumors.
- To evaluate the pharmacokinetics (PK) of 2X-121 monotherapy (Part 1) and in combination with dovitinib (Part 2) in patients with advanced solid tumors.
- To evaluate the safety and tolerability of 2X-121 monotherapy (Part 1) and in combination with dovitinib (Part 2) in patients with advanced solid tumors.

2.2. STUDY OUTCOME MEASURES

2.2.1. Primary Outcome Measure

The primary outcome measures in this study are:

Part 1

- Determination of the MTD of 2X-121 monotherapy.

Note: The MTD is defined as 1 dose level below the dose in which dose limiting toxicities (DLTs) were observed in $\geq 33\%$ of the participants during the first 14 days of the main treatment period.

Part 2

- Determination of the MTD of dovitinib given in combination with 2X-121 (MTD).

Note: The MTD is defined as 1 dose level below the dose in which dose limiting toxicities (DLTs) were observed in $\geq 33\%$ of the participants during the first 14 days of the main treatment period.

2.2.2. Secondary Outcome Measures

2.2.2.1. Antitumor Activity

The secondary anti-tumor activity outcome measures in this study are:

- To evaluate the objective response rate (ORR) of 2X-121 monotherapy (Part 1) and in combination with dovitinib (Part 2).

ORR is defined as the proportion of subjects who achieve a Complete Response (CR) or Partial Response (PR) as assessed by RECIST v1.1.

- To evaluate the duration of overall response (DOR) of 2X-121 monotherapy (Part 1) and in combination with dovitinib (Part 2).

DOR is defined as the time in months from the first documented CR or PR per RECIST v. 1.1 to disease recurrence or disease progression (PD) whichever occurs first.

- To evaluate progression free survival (PFS) of 2X-121 monotherapy (Part 1) and in combination with dovitinib (Part 2).

PFS is defined as the time from study treatment initiation to either first observation of progressive disease or occurrence of death.

- To evaluate overall survival (OS) of 2X-121 monotherapy (Part 1) and in combination with dovitinib (Part 2).

OS is defined as the time from study treatment initiation to death from any cause or last day known to be alive.

2.2.2.2. Pharmacokinetic (PK) Outcome Measures

The following pharmacokinetic parameters will be calculated for 2X-121 monotherapy at each dose level (Part 1) and for 2X-121 (MTD) in combination with dovitinib at each dose level (Part 2):

- Maximum concentration of 2X-121 (C_{max}) and dovitinib (C_{max})
- Area under the plasma-time concentration curve (AUC)
- Elimination half-life of 2X-121 ($t_{1/2}$) and dovitinib ($t_{1/2}$)
- Time to maximum plasma concentration (t_{max})
- Total body clearance of 2X-121 (Cl/F) and dovitinib (Cl/F)

- Apparent volume of distribution (V_z/F)

2.2.2.3. Safety Outcome Measures

The safety and overall tolerability of 2X-121 and dovitinib will be evaluated based on:

- Dose Limiting Toxicities
- Incidence and severity of treatment-emergent adverse events (TEAEs), including serious adverse events and adverse events resulting in permanent discontinuation of study treatment
- Laboratory data changes from baseline to subsequent scheduled visits
- Changes in physical examinations from baseline to subsequent scheduled visits
- Changes in vital signs from baseline to subsequent scheduled visits
- Changes in Eastern Cooperative Oncology Group (ECOG) performance status from baseline to subsequent scheduled visits
- Changes of electrocardiogram (ECG) results from baseline to subsequent scheduled visits

[REDACTED]

[REDACTED]

[REDACTED]

[REDACTED]

3. STUDY DESIGN

3.1. GENERAL SCHEMA

This is a Phase Ib, two-part, multi-center study. In Part 1, the study will evaluate the safety and tolerability, antitumor activity, pharmacokinetics, and determine the maximum tolerated dose (MTD) of 2X-121 monotherapy (at BID regimen) in patients with advanced solid tumors. In Part 2, the study will evaluate safety and tolerability, antitumor activity, and pharmacokinetics of 2X-121 (MTD) and dovitinib as combination therapy, and determine the MTD of dovitinib when given in combination with the MTD of 2X-121 determined in Part 1.

Part 1

This part of the study will follow an accelerated titration method followed by a standard “3+3” design to determine the MTD of 2X-121. The MTD is defined as one dose level (cohort) below the dose in which dose limiting toxicities (DLTs) were observed in $\geq 33\%$ of the participants.

The calculation of the sample size for this trial is based on the traditional 3 + 3 dose escalation scheme which is conducted as follows:

- Subjects are treated in cohorts of one (Cohort 1) or three (Cohorts 2-3) subjects, each receiving the same dose. For the assessment of a DLT, subjects are observed for 14 days.
- In Cohort 1, if the one subject does not exhibit a DLT, the next cohort of three subjects will receive the next higher dose (Cohort 2). In Cohort 2, if none of the three subjects exhibits a DLT, the next cohort of three subjects will receive the next higher dose (Cohort 3).
- Otherwise, if at least one subject of a cohort exhibits a DLT, a further cohort of three subjects is treated at the same dose level (cohort) without escalating the dose.
- If exactly one out of the six subjects treated at this dose exhibits a DLT, the trial continues as planned at the next higher dose level (cohort).
- If two or more subjects out of the six subjects treated at this dose exhibit a DLT, the dose escalation stops at that level and the next lower dose is considered as the MTD. When the escalation has stopped, additional subjects will be treated at the MTD to a total of six subjects.

[REDACTED]

[REDACTED]

[REDACTED]

[REDACTED]

[REDACTED]

[REDACTED]

[REDACTED]

[REDACTED]

[REDACTED]

[REDACTED]

[figure not shown]
[REDACTED]

- [REDACTED]
[REDACTED]
- [REDACTED]
[REDACTED]
- [REDACTED]
- [REDACTED]
[REDACTED]
- [REDACTED]
[REDACTED]
- [REDACTED]
[REDACTED]

Part 2

In Part 2 of the study, patients will receive dovitinib in combination with the MTD of 2X-121 determined in Part 1. Part 2 will follow a “3+3” design to determine the MTD of dovitinib when given in combination with 2X-121. The MTD is defined as one dose level (cohort) below the dose in which dose limiting toxicities (DLTs) were observed in $\geq 33\%$ of the participants. See Part 1 above for definition of DLTs.

[REDACTED]

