- Otherwise, if at least one subject of a cohort exhibits a DLT, a further cohort of three subjects is treated at the same dose level (cohort) without escalating the dose.
- If exactly one out of the six subjects treated at this dose exhibits a DLT, the trial continues as planned at the next higher dose level (cohort).
- If two or more subjects out of the six subjects treated at this dose exhibit a DLT, the dose escalation stops at that level and the next lower dose is considered as the MTD. When the escalation has stopped, additional subjects will be treated at the MTD to a total of six subjects.

[REDACTED]

[REDACTED]

[REDACTED]

[REDACTED]

[REDACTED]

[REDACTED]

[REDACTED]

[REDACTED]

[REDACTED]

[REDACTED]

Name of Sponsor/Company:

Allarity Therapeutics, Inc

Name of Study Product: 2X-121

Investigational Combination Therapy: 2X-121 + dovitinib

Protocol Number:

Protocol #AL-2003

Indication:

Advanced Solid Tumors

- [REDACTED]
- [REDACTED]
- [REDACTED]
- [REDACTED]
- [REDACTED]
- [REDACTED]
- [REDACTED]
- [REDACTED]
- [REDACTED]
- [REDACTED]

The dose levels to be evaluated in Part 1 are shown below:

Dose Cohort	2X-121 Monotherapy Dose (BID)
Cohort 1	600 mg (morning dose: 200 mg + evening dose: 400 mg)
Cohort 2	800 mg (morning dose: 400 mg + evening dose: 400 mg)
Cohort 3	1000 mg (morning dose: 400 mg + evening dose: 600 mg)

On Day 1 of first treatment cycle (C1D1), patients will be administered 2X-121 monotherapy as oral capsules taken twice daily. Each treatment cycle will consist of 28 days.

- [REDACTED]
- [REDACTED]
- [REDACTED]
- [REDACTED]
- [REDACTED]
- [REDACTED]

Once the MTD has been determined, subjects enrolled in lower dose cohorts will be allowed to escalate the dose to the MTD, if acceptable per the Investigator's discretion. Subjects will be eligible for continuing treatment in absence of progressive disease or unacceptable toxicity or withdrawal of consent.

Part 2

In Part 2 of the study, patients will receive dovitinib in combination with the MTD of 2X-121 determined in Part 1. Part 2 will follow a "3+3" design to determine the MTD of dovitinib when given in combination with 2X-121. The MTD is defined as one dose level (cohort) below the dose in which dose limiting toxicities (DLTs) were observed in $\geq 33\%$ of the participants. See Part 1 above for definition of DLTs.

Name of Sponsor/Company:

Allarity Therapeutics, Inc

Name of Study Product: 2X-121

Investigational Combination Therapy: 2X-121 + dovitinib

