5.2.2. Subject Replacement

This study will follow a 3+3 design during Part 1 and Part 2. Three subjects within a dose level must be observed for one cycle (14 days) before accrual to the next higher dose level may begin. If a subject is withdrawn from the study prior to completing one cycle of therapy for any reason other than experiencing a DLT, an additional subject may be added to that dose level.

Note: Subjects who discontinue treatment prior to completing one cycle of therapy due to experiencing a DLT will not be replaced.

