8.2.1.1 Maximum Tolerated Dose (MTD)

The MTD is defined as the highest dose that does not produce unacceptable toxicity, or 1 dose level below the dose in which dose limiting toxicities (DLTs) were observed in \geq 33% of the participants during the first 14 days of the main treatment period.

MTD will be determined by sponsor in consultation with the safety assessment committee.

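### Part 1, Cohorts 2 and 3: the printed escalation list expands after 2/3 or 3/3 DLTs, dosing three more subjects at a level already bound to be rejected

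*Protocol*

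**What the plan says.** The Part 1 list in Protocol 3.1 has four steps that matter here.

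- **Escalate:** "In Cohort 2, if none of the three subjects exhibits a DLT, the next cohort of three subjects will receive the next higher dose".
- **Expand:** in all other cases, "if at least one subject of a cohort exhibits a DLT, a further cohort of three subjects is treated at the same dose level".
- **Continue after expansion:** "If exactly one out of the six subjects treated at this dose exhibits a DLT, the trial continues as planned".
- **Stop after expansion:** "If two or more subjects out of the six subjects treated at this dose exhibit a DLT, the dose escalation stops at that level". In that case the MTD is set one level down, and that level is filled to six subjects.

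The Protocol synopsis and SAP 2.1.1 repeat the expansion trigger in the same words. The protocol writes the no-DLT branch for Cohort 2 only, and the SAP writes it for Cohorts 2-3. The expansion bullet refers to any cohort, so it covers Cohort 3 in both documents.

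Protocol 2.2.1 adds: "The MTD is defined as 1 dose level below the dose in which dose limiting toxicities (DLTs) were observed in" at least 33% of participants in the first 14 days. SAP 8.2.1.1 adds that "MTD will be determined by sponsor in consultation with the safety assessment committee".

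**The concern.** A 3+3 rule expands a cohort when the first three subjects leave the decision open. One DLT in three does that. Two or three DLTs do not, because the level already has enough DLTs to fail under the list's own stop rule. The printed list treats all three results alike.

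Followed literally, a site would enrol three more patients at a dose known to be failing. Nothing they show could rescue the dose. Declaring the MTD, and filling the lower level to six, would wait for another DLT window. What is at stake is avoidable patient exposure and delay. The validity of the MTD is not affected.

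**Working it through.** **Inputs.** Cohorts 2 and 3 start with three subjects and expand by three; continue at 1/6; stop at 2/6 or more; 14-day DLT window (Protocol 3.1). Maxima are 16 and 24 (Protocol 8.3). True DLT rates are not given, so *p* = 10% to 50% is assumed, with independent subjects.

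**The plan's own maxima.** Part 1: (1+3) + (3+3) + (3+3) = 4 + 6 + 6 = 16, as stated. Part 2: three levels of six plus the upper end of the additional 3-6 patients gives 18 + 6 = 24, as stated.

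**Is rejection certain?** After 2/3, the total of six can only be 2, 3, 4 or 5. After 3/3, it can only be 3, 4, 5 or 6. Exactly one is impossible and two or more is guaranteed.

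**How often can it happen?** The event ends escalation, so at most once in Part 1: three subjects.

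**Probability at one level.** q(p) = P(2 or 3 DLTs in 3) = 3p²(1−p) + p³. At p = 0.3: 3(0.09)(0.7) + 0.027 = 0.216.

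**Probability that a level passes.** s(p) = (1−p)³ + 3p(1−p)²·(1−p)³ = (1−p)³ + 3p(1−p)⁵. At p = 0.3: 0.343 + 0.9(0.16807) = 0.494.

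**Part 1, given that Cohort 2 opens.** P(event) = q(p₂) + s(p₂)·q(p₃). At 30% for both: 0.216 + 0.494 × 0.216 = 0.323. Expected extra subjects are 3·P(event). With equal rates, expected extra DLTs are 3p·P(event).

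| Rate at both levels | q(p) | s(p) | P(event) | Extra subjects | Extra DLTs |
|---|---|---|---|---|---|
| 10% | 2.8% | 0.906 | 5.3% | 0.16 | 0.02 |
| 20% | 10.4% | 0.709 | 17.8% | 0.53 | 0.11 |
| 30% | 21.6% | 0.494 | 32.3% | 0.97 | 0.29 |
| 40% | 35.2% | 0.309 | 46.1% | 1.38 | 0.55 |
| 50% | 50.0% | 0.172 | 58.6% | 1.76 | 0.88 |

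With rates rising from Cohort 2 to Cohort 3, P(event) is 12.2% (10%/20%), 25.7% (20%/30%), 35.3% (20%/40%) and 46.3% (30%/50%). When the event occurs, the three extra subjects have 3p expected DLTs: 0.3 at 10%, 0.9 at 30%, 1.5 at 50%.

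**Does stopping at 2/3 change the result?** The two rules differ only after 2/3 or 3/3, and both then reject the level. Enumerating all 4⁴ = 256 combinations of DLT counts (first three and further three, Cohorts 2 and 3) gives no change in the MTD decision, a saving of 0 or 3 subjects, and a maximum of 12 for the two cohorts under either rule. Because 1/3 still expands to six, 16 and 24 stand.

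**The case against.** The strongest reply is that the halt may exist where it cannot be read. Text after the Part 1 list is redacted, as is Protocol 5.3 on stopping criteria, and Protocol Figure 3-1 and SAP Figure 2.1 are not shown. The plan also calls the design a standard 3+3. This stands as a limit: the point concerns the printed list and does not prove that no halt exists. It does not excuse the list, which appears three times and would then conflict with the hidden text on when to stop dosing.

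The safety assessment committee in SAP 8.2.1.1 might intervene. The visible text gives it a consulting role on the MTD and says nothing about halting enrolment. Protocol 5.2.2 does not help either: "Three subjects within a dose level must be observed for one cycle (14 days) before accrual to the next higher dose level may begin". That governs escalation, not expansion at the same level.

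The 33% definition is weak support. A result of 2/3 (67%) meets it, but so does 1/3 (33.3%), which the list rightly expands. The case therefore rests on the continue and stop bullets.

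The probabilities use assumed rates and condition on Cohort 2 opening. If Cohort 1 has the same rate and passes at 0/1 or 1/4 (an assumption), it passes with probability (1−p) + p(1−p)³, which is 0.803 at 30% and 0.5625 at 50%. The unconditional figures are then 0.803 × 32.3% ≈ 26% and 0.5625 × 58.6% ≈ 33%. They are smaller but not negligible.

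Finally, the expansion bullet is also the only visible instruction for a DLT in single-subject Cohort 1, so a careless rewrite would remove it. That is a fair warning about drafting, and the fix below allows for it.

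**Conclusion.** The concern holds for the printed rule in Part 1, Cohorts 2 and 3. After 2/3 or 3/3 DLTs the list sends three more subjects to a dose that its own stop rule must reject. The harm is bounded at one occurrence, three subjects and at least one further 14-day window. The certainty of rejection follows from the listed bullets alone; only the frequency depends on assumed DLT rates.

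This should be corrected because it concerns patient exposure with no decision value. It is not critical, since MTD selection and the maximum sample sizes are unaffected. Confidence is medium because of the redacted text and missing figures. Part 2 is affected only if it uses the same list: the visible text calls it 3+3 and refers back to Part 1 only for the DLT definition.

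**What to change.** In the Protocol synopsis, Protocol 3.1 and SAP 2.1.1:

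1. Expand a three-subject cohort only if exactly one of the three has a DLT.
2. Once two or more subjects at such a level have a DLT, stop enrolling there and take the next lower dose as the MTD. This also covers a second DLT during an expansion, a saving not counted above.
3. Keep the existing Cohort 1 expansion as its own sentence.
4. Leave subjects already on treatment under the present rule: "Subjects will be eligible for continuing treatment in absence of progressive disease or unacceptable toxicity or withdrawal of consent".
5. Check Protocol Figure 3-1, SAP Figure 2.1 and the redacted stopping text for agreement. If Part 2 uses this list, say so and apply the same wording.

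The cost is a protocol amendment and a SAP edit in three visible places, plus the consistency check. No subjects are added, and three fewer are dosed whenever 2/3 or 3/3 occurs in Cohort 2 or 3.
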